- 3.2.12 Patients are allowed to receive, but not required to receive, up to 4 additional lines of therapy.
- 3.2.13 At least 4 weeks must have elapsed since the patient underwent any major surgery (e.g., major: laparotomy, laparoscopy) There is no delay in treatment for minor procedures (e.g., tumor FNA or core biopsy, venous access device placement).

- 3.2.14 Have demonstrated adequate organ function as defined in Table 1. All screen labs should be performed within 14 days of treatment initiation
- Table 1
 Adequate Organ Function Laboratory Values

System	Laboratory Value		
Hematological			
Absolute neutrophil count (ANC)	≥1,500 /mcL		
Platelets	≥100,000 / mcL		
Hemoglobin	\geq 9 g/dL or \geq 5.6 mmol/L without transfusion or EPO dependency (within 7 days of assessment)		
Renal			
Serum creatinine OR	≤1.5 X upper limit of normal (ULN) OR		
Measured or calculated ^a creatinine			
clearance	\geq 60 mL/min for subject with creatinine levels > 1.5 X		
(GFR can also be used in place of	institutional ULN		
creatinine or CrCl)			
Hepatic			
Serum total bilirubin	≤ 1.5 X ULN OR		
	Direct bilirubin \leq ULN for subjects with total bilirubin levels $>$		

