4.2.2 Dose Modification (Escalation/Titration/Other)

Adverse events (both non-serious and serious) associated with pembrolizumab exposure may represent an immunologic etiology. These adverse events may occur shortly after the first dose or several months after the last dose of treatment. Pembrolizumab must be withheld for drug-related toxicities and severe or life-threatening AEs as per Table below.

irAE Toxicity	Hold Treatment For Grade	Timing for Restarting Treatment	Treatment Discontinuation		
Diarrhea/Colitis	2-3	Toxicity resolves to Grade 0-1	Toxicity does not resolve within 12 weeks of last dose or inability to reduce corticosteroid to 10 mg or less of prednisone or equivalent per day within 12 weeks		
	4	Permanently discontinue	Permanently discontinue		
AST, ALT, or	2	Toxicity resolves to Grade 0-1	Toxicity does not resolve within 12 weeks of last dose		
Bilirubin	3-4	Permanently discontinue (see exception below) ^a	Permanently discontinue		
Type 1 diabetes mellitus (if new onset) or Hyperglycemia	T1DM or 3-4	Hold pembrolizumab for new onset Type I diabetes mellitus or Grade 3-4 hyperglycemia associated with evidence of beta cell failure	Resume pembrolizumab when patients are clinically and metabolically stable		

Table 4 Dose Modification Guidelines for Drug-Related Adverse Events

	1	1	
irAE Toxicity	Hold Treatment For Grade	Timing for Restarting Treatment	Treatment Discontinuation
Hypophysitis	2-4	Toxicity resolves to Grade 0-1. Therapy with pembrolizumab can be continued while endocrine replacement therapy is instituted	Toxicity does not resolve within 12 weeks of last dose or inability to reduce corticosteroid to 10 mg or less of prednisone or equivalent per day within 12 weeks
Hyperthyroidism	3	Toxicity resolves to Grade 0-1	Toxicity does not resolve within 12 weeks of last dose or inability to reduce corticosteroid to 10 mg or less of prednisone or equivalent per day within 12 weeks
	4	Permanently discontinue	Permanently discontinue
Hypothyroidism		Therapy with pembrolizumab can be continued while thyroid replacement therapy is instituted	Therapy with pembrolizumab can be continued while thyroid replacement therapy is instituted
	2 ^b	Toxicity resolves to Grade 0-1	Permanently discontinue if toxicity develops despite adequate premedication ^d
Infusion Reaction	3-4	Permanently discontinue	Permanently discontinue

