4.3 Timing of Dose Administration

Trial treatment should be administered on Day 1 of each cycle after all procedures/assessments have been completed as detailed on the Trial Flow Chart. Trial treatment may be administered up to 3 days before or after the scheduled Day 1 of each cycle due to administrative reasons.

All trial treatments will be administered on an outpatient basis.

Pembrolizumab 200 mg will be administered as a 30 minute IV infusion every 3 weeks. Sites should make every effort to target infusion timing to be as close to 30 minutes as possible. However, given the variability of infusion pumps from site to site, a window of -5 minutes and +10 minutes is permitted (i.e., infusion time is 30 minutes: $-5 \min/+10 \min$).

The Pharmacy Manual contains specific instructions for the preparation of the pembrolizumab infusion fluid and administration of infusion solution.

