- When symptoms improve to Grade 1 or less, steroid taper should be started and continued over no less than 4 weeks.
- Type 1 diabetes mellitus (if new onset, including diabetic ketoacidosis [DKA]) or ≥ Grade 3 Hyperglycemia, if associated with ketosis (ketonuria) or metabolic acidosis (DKA)
 - For **T1DM** or **Grade 3-4** Hyperglycemia
 - Insulin replacement therapy is recommended for Type I diabetes mellitus and for Grade 3-4 hyperglycemia associated with metabolic acidosis or ketonuria.
 - Evaluate patients with serum glucose and a metabolic panel, urine ketones, glycosylated hemoglobin, and C-peptide.
- Hypophysitis:

- For **Grade 2** events, treat with corticosteroids. When symptoms improve to Grade 1 or less, steroid taper should be started and continued over no less than 4 weeks. Replacement of appropriate hormones may be required as the steroid dose is tapered.
- For **Grade 3-4** events, treat with an initial dose of IV corticosteroids followed by oral corticosteroids. When symptoms improve to Grade 1 or less, steroid taper should be started and continued over no less than 4 weeks. Replacement of appropriate hormones may be required as the steroid dose is tapered.

• Hyperthyroidism or Hypothyroidism:

Thyroid disorders can occur at any time during treatment. Monitor patients for changes in thyroid function (at the start of treatment, periodically during treatment, and as indicated based on clinical evaluation) and for clinical signs and symptoms of thyroid disorders.

- Grade 2 hyperthyroidism events (and Grade 2-4 hypothyroidism):
 - In hyperthyroidism, non-selective beta-blockers (e.g. propranolol) are suggested as initial therapy.
 - In hypothyroidism, thyroid hormone replacement therapy, with levothyroxine or liothyroinine, is indicated per standard of care.
- Grade 3-4 hyperthyroidism
 - Treat with an initial dose of IV corticosteroid followed by oral corticosteroids. When symptoms improve to Grade 1 or less, steroid taper should be started and continued over no less than 4 weeks. Replacement of appropriate hormones may be required as the steroid dose is tapered.
- Hepatic:
 - For **Grade 2** events, monitor liver function tests more frequently until returned to baseline values (consider weekly).
 - Treat with IV or oral corticosteroids
 - For Grade 3-4 events, treat with intravenous corticosteroids for 24 to 48 hours.
 - When symptoms improve to Grade 1 or less, a steroid taper should be started and continued over no less than 4 weeks.

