4.8 Subject Withdrawal/Discontinuation Criteria

Subjects may withdraw consent at any time for any reason or be dropped from the trial at the discretion of the investigator should any untoward effect occur. In addition, a subject may be withdrawn by the investigator or the Sponsor if enrollment into the trial is inappropriate, the trial plan is violated, or for administrative and/or other safety reasons.

A subject must be discontinued from the trial for any of the following reasons:

• The subject or legal representative (such as a parent or legal guardian) withdraws consent. Version 9.0, 26 April 2023

- Confirmed radiographic disease progression
- Intercurrent illness that prevents further administration of treatment
- Investigator's decision to withdraw the subject
- The subject has a confirmed positive serum pregnancy test
- Noncompliance with trial treatment or procedure requirements
- The subject is lost to follow-up
- Completed 24 months of uninterrupted treatment with pembrolizumab or 35 administrations of study medication, whichever is later.

Note: 24 months of study medication is calculated from the date of first dose. Subjects who stop pembrolizumab after 24 months may be eligible for up to one year of additional study treatment if they progress after stopping study treatment.

- Administrative reasons
- In case of radiographic complete response confirmed with 2 consecutive CAT scans 12 weeks apart, patient may be discontinued from study.

After the end of treatment, each subject will be followed for 30 days for adverse event monitoring (serious adverse events will be collected for 90 days after the end of treatment). Subjects who discontinue for reasons other than progressive disease will have post-treatment follow-up for disease status until disease progression, initiating a non-study cancer treatment, withdrawing consent or becoming lost to follow-up. After documented disease progression each subject will be followed by telephone for overall survival until death, withdrawal of consent, or the end of the study, whichever occurs first.

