6.0 STUDY PARAMETERS

The Trial Flow Chart - Section 6.0 summarizes the trial procedures to be performed at each visit. Individual trial procedures are described in detail below. It may be necessary to perform these procedures at unscheduled time points if deemed clinically necessary by the investigator.

6.1 Observations and Tests

The following observations and tests are to be performed and recorded before, during, and after treatment (**Table 6: Study Calendar**):

	Pre-Treatment	Treatment Period	Treatment Period	End of treatment visit
Study week		Cycle 1	Cycle 2 and higher	
Cycle Day		21	21	
Study Procedures Window	(-28 to 1 Days)	± 3	± 3	
History, PE, Performance Status, Toxicity Evaluation, weight	X	X	*** X	X
CBC /Diff/Platelets	Х	Х	***X	X
Chemistries:Serum Cr,BUN,K,Mg,Bili	X	X	***X	X
PT/INR and aPTT	Х			
Urinalysis	X		****as clinically indicated	****as clinically indicated
SGOT,SGPT,Alk Phos	Х	Х	Х	X
Vital signs	X	Х	Х	X
EKG	Х		****as clinically indicated	****as clinically indicated
Toxicity	X	Х	X	X

	Pre-Treatment	Treatment Period	Treatment Period	End of treatment visit
Study week		Cycle 1	Cycle 2 and higher	
Cycle Day		21	21	
Study Procedures Window	(-28 to 1 Days)	±3	± 3	
History, PE, Performance Status, Toxicity Evaluation, weight	X	X	*** X	X
CBC /Diff/Platelets	Х	Х	***X	X
Chemistries:Serum Cr,BUN,K,Mg,Bili	Х	Х	***X	Х
PT/INR and aPTT	Х			
******Radiographic tumor evaluation and measurement (Chest/Abd/Pelvis)	Х		X	
*CA 125	X		X	
*TSH	X		X	
** collection of blood for Translational Studies	X		Every other cycle after study initiation	X

- * CA 125, and TSH should be performed after 6 weeks (end of cycle 2), 12 weeks (end of cycle 4), and every 12 weeks thereafter until end of treatment on protocol. CA 125 shall be performed per standard of care following end of treatment per protocol. TSH shall be performed per endocrinologist/PCP for thyroid toxicities.
- ** See Appendix C for collection and shipping information.
- *** All activities performed every 3 weeks
- **** During the treatment period, EKG and urinalysis will be performed on screening and as clinically Indicated thereafter.
- ***** All screen labs should be performed within 14 days of treatment initiation. Laboratory assessments at Cycle 1 Day 1 are not required if the previous screen labs are within 14 days prior to treatment initiation.

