- ***** Repeat CT scan or MRI should use similar equipment and techniques to ensure consistent measurements. Tumor evaluation should be performed after 6 weeks (end of cycle 2), 12 weeks (end of cycle 4), and every 12 weeks (+/- 14 days) thereafter.

The screening procedures include:

- A review of the patient medical history including a list of current medications and dosing schedules, previous therapies for disease, and residual treatment toxicities.
- Physical examination, height, weight and vital signs (pulse, temperature, respiration, and blood pressure). A pelvic examination may be required if this method is used to measure patients disease.
- An electrocardiogram (ECG) will be performed for baseline assessment.
- A CT scan of chest, abdomen and pelvis will be performed or an MRI if necessary. The scans may not have to be repeated if performed within 28 days.
- Blood test for CA 125
- Blood test for thyroid-stimulating hormone (TSH)
- Lab work: CBC, Chemistry (electrolyte, magnesium, SGOT, SGPT, Alk. Phos), Coagulation (PT/INR and aPTT)

- Approximately 3 teaspoons (20 mL) of blood will be collected to evaluate the number and activation of B cells, T cells and NK cells
- woman of child-bearing potential, a pregnancy test will be performed from either urine or blood sample.

Treatment Procedures:

The following will take place at different times during the treatment period:

- At each study visit (every 3 weeks) a physical examination including weight and vital signs (pulse, temperature, respirations and blood pressure). A pelvic examination may be required if this method is used to measure your disease.
- Toxicity assessment (weekly during first cycle of treatment)
- Routine lab work such as complete blood count, serum chemistries, and electrolytes will be obtained
- A CT or MRI of the chest abdomen and pelvis will be performed after 6 weeks, 12 weeks, and every 12 weeks (+/- 14 days) thereafter or as medically indicated thereafter.
- Blood test for CA 125 Protein levels, and TSH will be drawn after 6 weeks, 12 weeks, and every 12 weeks thereafter until end of treatment on protocol.
- Blood samples to test the number and activation of different subsets of lymphocytes will be collected at baseline and every other cycle.

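### The protocol mandates a hold for new-onset type 1 diabetes or Grade 3-4 hyperglycemia with beta cell failure, but names no scheduled glucose test; separately, the albumin entry limit is printed in a unit that excludes nobody

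*Combined protocol and SAP*

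**What the plan says.** **Hold rule.** Section 4.2.2 makes the Table 4 holds mandatory. The diabetes row reads "Hold pembrolizumab for new onset Type I diabetes mellitus or Grade 3-4 hyperglycemia associated with evidence of beta cell failure".

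**Dosing condition.** Section 4.3 says "Trial treatment should be administered on Day 1 of each cycle after all procedures/assessments have been completed as detailed on the Trial Flow Chart". The calendar it relies on is Table 6 in section 6.1.

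**Scheduled tests.** The Table 6 chemistry row, printed twice with the same analytes, is "Chemistries:Serum Cr,BUN,K,Mg,Bili". A separate row covers AST, ALT and alkaline phosphatase. TSH has its own row. Urinalysis is done at screening and afterwards only when clinically indicated. The screening list in the same section gives "Lab work: CBC, Chemistry (electrolyte, magnesium, SGOT, SGPT, Alk. Phos), Coagulation (PT/INR and aPTT". The on-treatment text is looser: "Routine lab work such as complete blood count, serum chemistries, and electrolytes will be obtained".

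**Where glucose is named.** Section 4.6.1, for patients with type 1 diabetes or Grade 3-4 hyperglycemia: "Evaluate patients with serum glucose and a metabolic panel, urine ketones, glycosylated hemoglobin, and C-peptide".

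**Entry.** The note under section 3.3.8 lets patients with type 1 diabetes enrol.

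**Albumin.** Section 3.2.14 requires that patients "Have demonstrated adequate organ function as defined in Table 1". Table 1 prints the albumin limit as at least 2.5 mg/dL. No other section gives an albumin limit.

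**The concern.** Hyperglycemia is a laboratory finding. A mandatory hold that depends partly on it would normally have a scheduled test behind it, and here none is named. Section 4.3 ties each dose to completing the calendar assessments, so the calendar is where a site looks to see what must be in hand before infusing.

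The missing baseline matters for a second reason. The hold turns on new onset, yet patients with existing type 1 diabetes may enrol, and a pre-treatment glucose helps to separate new or worsening disease from what was already there.

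The albumin point is independent of this. An entry criterion that every patient passes does no work, and a limit in the wrong unit leaves the eligibility check to infer what was meant.

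**Working it through.** The glucose point is a comparison of texts; the albumin point is a unit conversion.

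**1. Laboratory-based rows of Table 4 against the Table 6 schedule**

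| Table 4 row | Test named in Table 6 | When |
|---|---|---|
| AST, ALT or bilirubin | AST, ALT, bilirubin | Screening and each cycle |
| Nephritis, graded on creatinine or acute kidney injury | Serum creatinine | Screening and each cycle |
| Hyper- and hypothyroidism | TSH | Screening, weeks 6 and 12, then every 12 weeks |
| Type 1 diabetes or hyperglycemia | None | Not scheduled |

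The liver, renal and thyroid rows each have a scheduled test. The diabetes row does not.

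**2. Can the dosing condition be met without a glucose result?** Section 4.3 asks for the calendar procedures to be complete. They include history, examination, toxicity evaluation, blood count, the five listed chemistries and the liver enzymes. A site that does exactly these has complied, with no glucose at baseline or in any cycle.

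**3. What would a scheduled glucose do?** It would not decide the hold. For hyperglycemia the hold also needs evidence of beta cell failure, which comes from the section 4.6.1 work-up (C-peptide, ketones and the rest). A scheduled value would prompt that work-up in a patient without symptoms.

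**4. Albumin.** Input: 2.5 mg/dL, from Table 1.
- Conversion: 2.5 mg/dL ÷ 1,000 = 0.0025 g/dL.
- Against a limit of 2.5 g/dL: 2.5 ÷ 0.0025 = 1,000, so the printed limit is 1,000 times lower.
- The documents give no albumin range. Assume that values in living patients run from about 1 to 5 g/dL. Then 1 ÷ 0.0025 = 400 and 5 ÷ 0.0025 = 2,000, so real values lie 400 to 2,000 times above the printed limit.
- Values of 1.0, 1.5, 2.0 and 2.4 g/dL all pass as printed and would all fail at 2.5 g/dL.
- Hemoglobin, in the same table, is limited in g/dL.

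**5. Effect on the design.** Neither glucose nor albumin enters the two-stage calculation. As a background check, exact binomial probabilities under the Table 8 rules, averaged uniformly over first-stage sizes 8 to 15 and cumulative sizes 18 to 25, compare with section 11.3 as follows:

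| Quantity | Recomputed | Stated |
|---|---|---|
| Average alpha at 5% response | 9.45% | 9.5% |
| Probability of early termination at 5% | 64.9% | 64.9% |
| Expected sample size at 5% | 15.13 | 15.14 |
| Average power at 25% response | 90.05% | 90.0% |

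The stated figures reproduce.

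**The case against.** **Not named is not the same as not measured.** A reader might infer that glucose will go unmeasured in this trial. The documents do not support that. The on-treatment wording is open-ended, and a local chemistry panel may include glucose. Urinalysis is done at screening and when indicated. Toxicity is reviewed every cycle, and section 6.0 allows unscheduled tests. The screening list is also visibly incomplete: it omits creatinine and bilirubin, which Table 1 needs, so its silence on glucose is weak evidence taken alone. All of this stands. But Table 6 does name creatinine and bilirubin, and it does not name glucose. The other safeguards depend on local practice, symptoms or suspicion.

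**Other holds have no dedicated test either.** Pneumonitis and myocarditis are detected clinically and then worked up. That is fair as a description of the protocol's general approach. The closer comparison is with the rows that rest on a blood test, and those have one scheduled.

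**Dose counts.** A reader might infer 35 unmonitored doses per patient from "Completed 24 months of uninterrupted treatment with pembrolizumab or 35 administrations of study medication, whichever is later". That is a stopping limit. Treatment ends earlier on progression or intolerable toxicity, and up to a further year is possible after later progression. The count adds nothing to the point.

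**Albumin may be a harmless slip.** The number 2.5 is intact, g/dL stands in the same table, and most readers would see the intention. Section 3.3.16 also lets the investigator exclude a patient for a laboratory abnormality. The eligibility checklist used at registration is not in the documents and may carry the right unit. The neighbouring transaminase row is garbled in the text reviewed, so a reading fault in the albumin unit cannot be ruled out. It would therefore be too strong to infer that the criterion is unusable or that unfit patients were enrolled. What stands is that the limit, as it reads, screens out no one and is corrected nowhere else.

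**Conclusion.** Both points hold and both are minor.

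On glucose, the plan sets a mandatory hold without naming a scheduled test that would bring asymptomatic hyperglycemia to attention, and it requires no baseline value. The consequence is possible delay in detection. It is not a total loss of detection, since known diabetes should appear in the medical history and symptomatic cases should surface at the cycle visits. The documents give no rate from which delayed or missed events could be estimated, so no number is put on it.

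On albumin, the printed limit excludes nobody, given the assumption that real values are at least about 1 g/dL. That it was meant as g/dL is an inference from the hemoglobin row, and it assumes that the unit was read correctly from the source.

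The two points are separate, and neither supports the other. Neither changes the response endpoint, the error rates, the sample size or the futility rule.

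**What to change.** 1. Add glucose to both printings of the Table 6 chemistry row, at screening and at each cycle, and to the section 6.1 screening laboratory list. Leave the Table 4 hold rule and the section 4.6.1 work-up as they are.
2. Check the albumin unit in the source document and confirm the intended value with the sponsor, then correct Table 1, probably to 2.5 g/dL.

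The cost is one analyte on blood already being drawn, and one corrected unit. The downside is slightly more laboratory data to enter and some repeat tests for high non-fasting values.

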6.1.1 Administrative Procedures

6.1.1.1 Informed Consent

The Investigator must obtain documented consent from each potential subject prior to participating in a clinical trial.

General Informed Consent

Consent must be documented by the subject's dated signature or by the subject's legally acceptable representative's dated signature on a consent form along with the dated signature of the person conducting the consent discussion.

A copy of the signed and dated consent form should be given to the subject before participation in the trial.

The initial informed consent form, any subsequent revised written informed consent form and any written information provided to the subject must receive the IRB/ERC's approval/favorable opinion in advance of use. The subject or his/her legally acceptable representative should be informed in a timely manner if new information becomes available that may be relevant to the subject's willingness to continue participation in the trial. The communication of this information will be provided and documented via a revised consent form or addendum to the original consent form that captures the subject's dated signature or by the subject's legally acceptable representative.

Specifics about a trial and the trial population will be added to the consent form template at the protocol level.

The informed consent will adhere to IRB/ERC requirements, applicable laws and regulations and Sponsor requirements.

